8.2 Baseline Measurements

For all laboratory measures, the baseline value is the last assessment taken prior to randomization. When there is a missing baseline assessment it will not be imputed, thus, subjects are excluded from any changes from baseline analysis for which they have a missing baseline value.

8.3 Day Ranges for Analysis of Time Points

For this study, “Day 1” refers to the start of planned 3-4 drug systemic induction chemotherapy, and not necessarily the day of randomization or first dose of apixaban. Study visits are timed from the start of induction therapy. Subjects do not always adhere strictly to the visit schedule timing in the protocol.

The imaging data for the primary efficacy analysis for primary endpoint up to Day 40 will be included in analyses.

The day ranges for the analyses of laboratory and vital sign measurements are defined in Table 8.3-1.

Table 8.3-1: Day Ranges for Analysis of Vital Sign and Laboratory Measurements

Nominal Visit	Target Day	Day Ranges
Baseline	Pre-dose up to 2 days prior to randomization	Prior to or on the day of randomization
Day 8	8	Day 5 - 10, but exclude values prior to or on day of randomization
Day 15	15	Day 11 - 20

Table 8.3-2: Day Ranges for Analysis of Vital Sign and Laboratory Measurements

Day 22	22	Day 21 - 27
Day 29	29	Day 28 -34
Follow-up	35	Day 35 - 40

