For a subject who experiences a reaction to asparaginase during the infusion and has to switch to Erwinia asparaginase during the induction chemotherapy, it is recommended that the subject continue the study treatment. The percentage of the original asparaginase dose delivered will be collected in the patient chart and case report form.

A platelet count $\geq 20,000$ / μ L must be obtained within 24 hours prior to the first dose of apixaban. A subject may be transfused platelets per investigator's clinical judgment but may not be transfused solely to meet entry criteria.

Apixaban should be discontinued at least 24 hours prior to any planned lumbar puncture (LP) and resumed no sooner than 18-24 hours after the procedure. In the event of a traumatic lumbar puncture (defined in this protocol as a lumbar puncture with ≥ 10 red blood cells (RBCs)/ μ L of cerebrospinal fluid (CSF), apixaban should be held for 48 hours after the procedure.

For example, for a LP scheduled on the morning of Day 8, the Day 7 PM and Day 8 AM and PM doses of apixaban should be held and may be restarted the morning of Day 9. If a subject will receive an LP on Day 29, the last dose will be the AM dose on Day 28.

During the study treatment period, study visits will occur on Day 8 \pm 5 days, Day 15 \pm 5 days, Day 22 \pm 5 days and Day 29 \pm 5 days of planned 3-4 drug systemic induction chemotherapy. Windows for study visits after randomization will be \pm 5 days. The timing of these study visits will coincide with standard of care visits for pediatric subjects in induction chemotherapy. Visits will consist of reporting adverse events (including bleeding and secondary endpoints as described below), monitoring medication adherence and laboratory testing. On the Day 29 visit, imaging evaluation will occur for all randomized subjects except for those who are discontinued from protocol therapy. For those subjects randomized to apixaban, imaging evaluations will be performed within 3 days but no more than 5 days of discontinuing apixaban. For those subjects randomized to the standard of care arm, it would be preferred that the imaging evaluations be performed within three days but no more than 5 days from Day 29 (Day 24 to Day 34). The evaluation will include a) a bilateral Doppler ultrasound that will include imaging of the venous system in which the CVAD is placed and the similar location for the opposite side; and b) an echocardiogram to assess for right atrial

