^a Screening visit can occur up to 14 days prior to randomization. It can also occur at the treatment visit (Day 1 - 4±3) as long as the subject is eligible by medical history, clinical exam, and has the laboratory results back to confirm the inclusive parameters.

Table 5.1-2: Study Procedural Outline ACCL1333 / CV185155					
Procedure	During Treatment Days 7 ± 5 For in-patients only	During Treatment Days 8 ± 5, 15 ± 5, 22 ± 5	End of Treatment Day 29 ± 5 or early drug discontinuation^a	Follow-up Visit Day 35 ± 5	Notes
Concomitant Medication Assessment	X	X	X	X	If done on Day 7 do not need to repeat on Day 8
Safety Assessments					
Targeted Physical Examination	X	X	X		Includes organ systems pertinent to the subject's signs, symptoms, or adverse events, eg, assessment of signs of VTE or bleeding. If done on Day 7 do not need to repeat on Day 8
Vital Signs	X	X	X		Heart rate, BP, respiratory rate and temperature If done on Day 7 do not need to repeat on Day 8
Adverse Events Assessment	X	X	X	X	Collection of SAEs begins after signed consent Collection of non-serious AE begins after randomization
Laboratory Tests: CBC with Platelets, ALT, AST, and direct (conjugated) bilirubin	X	X	X		If done on Day 7 do not need to repeat on Day 8
Laboratory Tests during the LP RBC in the CSF		X	X		RBC in the CSF only taken at investigator defined LPs

Table 5.1-2: Study Procedural Outline ACCL1333 / CV185155					
Procedure	During Treatment Days 7 ± 5 For in-patients only	During Treatment Days 8 ± 5, 15 ± 5, 22 ± 5	End of Treatment Day 29 ± 5 or early drug discontinuationa	Follow-up Visit Day 35 ± 5	Notes
In-patient Pharmacokinetic (PK) and anti-Xa sample collection. See Section 5.5	X				For subjects receiving apixaban only. For inpatient, a pre-dose PK and anti-FXa sample may be taken 1 day prior to LP (prior to the day 7 AM dose if LP on day 8) followed by a PK and anti-FXa sample taken 1-4 hr post dose. If the subject is outpatient, follow alternate sample collection procedures.
Alternate PK sample and anti-Xa collection. See Section 5.5		X			For outpatients, random PK and anti-FXa samples may be obtained prior to LP procedures for example during the Day 8 ± 5 visit and during Day 15 ± 5 visits.
Efficacy Assessments					

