7.6.3 Laboratory Data

The frequency of subjects with laboratory marked abnormalities (MAs) during the Treatment Period based on pre-specified criteria will be tabulated by treatment group, for each analyte.

Laboratory measurements (for liver function only) and their changes from baseline will be summarized at baseline and at the end of study by treatment group.

Shift analysis will be performed to evaluate qualitative changes that occurred during the Treatment Period. Shift tables (for liver function only) will display, by treatment group, the frequency of subjects with the following combination of values at baseline and during the Treatment Period:

- no change (low to low: L-L, normal to normal: N-N, high to high: H-H)
- abnormal to normal (low to normal: L-N, high to normal: H-N)
- normal to abnormal (normal to low: N-L, normal to high: N-H)
- abnormal to abnormal (low to high: L-H, high to low: H-L),

where low refers to values that are $<LLN$, high refers to values that are $>ULN$ and normal refers to values in-between the normal limits. Two sets of shift tables will be presented:

- one for labs with MA criteria based on high values (regardless of whether the MA criteria also considers low values) - the post-dose value considered for the tabulation will be the largest value obtained during the Treatment Period;
- another for labs with MA criteria based on low values (regardless of whether the MA criteria also considers high values) - the post-dose value considered for the tabulation will be the smallest value obtained during the Treatment Period.

In addition, liver-related elevations and discontinuations will be tabulated by treatment group. The tabulation will include the number and proportion of subjects with

- post-dose elevation of AT $>3 \times ULN$ (AT refers to either one of ALT or AST)
- post-dose elevation of AT $>5 \times ULN$
- post-dose elevation of AT $>10 \times ULN$
- post-dose elevation of AT $>20 \times ULN$
- post-dose elevation of conjugated bilirubin $>2 \times ULN$
- post-dose elevation of AT $>3 \times ULN$ and conjugated bilirubin $>2 \times ULN$ on the same date
- Liver-related discontinuations

The number and proportion of subjects with post-dose elevations of AST, ALT, conjugated bilirubin, ALP, or CK will also be tabulated by treatment group including:

- AST elevations $>3 \times ULN$, $>5 \times ULN$, $>10 \times ULN$, or $>20 \times ULN$

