- ALT elevations $>3 \times ULN$, $>5 \times ULN$, $>10 \times ULN$, or $>20 \times ULN$
- AST or ALT elevations $>3 \times ULN$, $>5 \times ULN$, $>10 \times ULN$, or $>20 \times ULN$
- both AST and ALT elevations $>3 \times ULN$, $>5 \times ULN$, $>10 \times ULN$, or $>20 \times ULN$ on the same date
- ALP elevations $>2 \times ULN$
- CK $>10 \times ULN$

Similar tabulations for the number and proportion of subjects with elevations of AST, ALT, total bilirubin, ALP, or CK as described in the previous paragraph will be presented by treatment group and by nominal visit (including baseline).

The following considerations apply to all liver-related laboratory tabulations described above:

- AT elevation refers to ALT or AST elevations regardless of whether they occurred concomitantly
- elevations will be counted if they occur during the Treatment Period; Only values that meet the criteria and are larger than the baseline value will be included in the tabulations. If baseline

value is missing then all values for that particular lab that meet the criteria will be included in the tabulations.

- values will be counted towards the categories of “AST and ALT elevations”, or “AT and Total Bilirubin elevation” if both AST and ALT or both AT and Total Bilirubin, respectively, meet the criteria and at least one of the values in the component is larger than the baseline value.
- values will be counted towards the categories of “AST or ALT elevations” if either AST meets the criteria and is larger than the AST baseline value or ALT meets the criteria and is larger than the ALT baseline value.
- For each subject and lab or lab combination, the largest value measured during the Treatment Period will be counted for the Treatment Period summaries that do not take nominal visit into consideration
- For each subject and lab or lab combination, the largest value measured within each visit window during the Treatment Period will be counted for the summaries by nominal visit.

The number and proportion of subjects with decreased platelet counts to $<20,000/\text{mm}^3$ will be tabulated by treatment group and by nominal visit (including baseline) and by treatment group for all measurements during the Treatment Period. The following considerations apply to these summaries:

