8.4 Multiple Measurements

Laboratory Measurements

For tabulations of changes from baseline or shift analyses, if multiple laboratory measurements are obtained within the same nominal visit, then the measurement obtained on the day closest to the target day for that nominal visit will be used; in the case of a tie, the measurement obtained on the earlier day will be used in the analyses.

For tabulations of incidence of marked abnormalities (e.g. ALT >3xULN), if multiple laboratory measurements are obtained within the same nominal visit, then the worst measurement within the nominal visit window nominal visit will be used.

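### SAP 8.3 gives no row to post-randomization laboratory values on Days 2-4, and its cut points can leave the Day 29 row without a compliant end-of-treatment sample

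*SAP*

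**What the plan says.** **Visits.** The Protocol synopsis (Study Design) states: "Windows for study visits after randomization will be" ± 5 days. Protocol Table 5.1-2 repeats this in its column heads, "During Treatment Days 8 ± 5, 15 ± 5, 22 ± 5" and "End of Treatment Day 29 ± 5 or early drug discontinuation", and adds a Day 7 ± 5 visit for inpatients. Blood count with platelets, ALT, AST and direct bilirubin are due at each. Randomization may take place from Day 1 to Day 4 ± 3 (Protocol 5.1).

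**Analysis rows.** SAP 8.3 counts days from the same Day 1, the start of induction. It files values by day alone:
- Baseline: up to and including the day of randomization
- Day 8: "Day 5 - 10, but exclude values prior to or on day of randomization"
- Day 15: Days 11-20
- Day 22: Days 21-27
- Day 29: Days 28-34
- Follow-up: Days 35-40

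It gives no rule for a value that falls in no range, and none for using the recorded visit label.

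**Use of the rows.** SAP 7.6.3 tabulates liver elevations and platelet counts below 20,000 "by treatment group and by nominal visit (including baseline"). These tables take the worst value in each window. Liver values and their changes from baseline "will be summarized at baseline and at the end of study by treatment group"; the SAP does not define that time point. For changes from baseline, when several values share a row, SAP 8.4 says "then the measurement obtained on the day closest to the target day for that nominal visit will be used".

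**The concern.** The analysis ranges and the visit windows use the same day count but do not fit together in three places.

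1. The Day 8 row opens on Day 5, while a child can be randomized on Day 1 and have a compliant first on-study visit before Day 5. A value drawn then is neither baseline nor Day 8.
2. The boundaries between rows are not midway between targets, although SAP 8.4 itself chooses among values by closeness to target.
3. The first four days of the compliant end-of-treatment window belong to the Day 22 row, so a child who attended on time can have nothing in the Day 29 row.

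At stake are the by-visit platelet and liver tables, where counts from the first days after randomization to an anticoagulant would be missing, and the end-of-study liver change, whose content depends on a time point that is not defined.

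**Working it through.** **Check of the day arithmetic.** 29 - 5 = 24 and 29 + 5 = 34. The Protocol writes the same span for control-arm imaging: "no more than 5 days from Day 29 (Day 24 to Day 34"). The figure is reproduced.

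**Compliant days looked up in the SAP ranges** (window = target ± 5):

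| Visit | Compliant days | Filed under own row | Filed elsewhere |
|---|---|---|---|
| Day 7 (inpatient) | 2-12 | 5-10 (Day 8 row) | 2-4 none; 11-12 to Day 15 |
| Day 8 | 3-13 | 5-10 | 3-4 none; 11-13 to Day 15 |
| Day 15 | 10-20 | 11-20 | 10 to Day 8 |
| Day 22 | 17-27 | 21-27 | 17-20 to Day 15 |
| Day 29 | 24-34 | 28-34 | 24-27 to Day 22 |

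**The gap.** A value on or before the randomization day goes to Baseline, so the gap has 4 - r days for a child randomized on Day r. Randomization on Day 1 leaves Days 2-4 (three days), on Day 2 leaves Days 3-4, and on Day 3 leaves Day 4. For randomization on Days 4-7 there is no gap. Values in the gap are plausible apart from the scheduled visit. The Protocol requires a platelet count within 24 hours before the first apixaban dose; for a child randomized on Day 1 and first dosed on Day 3 or 4, that count can fall there. Protocol 5.3.7 also asks for counts at least twice a week in some children.

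**Cut points.** The midpoints are (8 + 15)/2 = 11.5, (15 + 22)/2 = 18.5 and (22 + 29)/2 = 25.5. The SAP cuts at 10/11, 20/21 and 27/28. So Day 11 is 3 days from target 8 and 4 from 15, but is filed under 15. Days 19 and 20 are 3 and 2 days from 22, and 4 and 5 from 15, but are filed under 15. Days 26 and 27 are 3 and 2 days from 29, and 4 and 5 from 22, but are filed under 22.

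**The Day 29 row.** Take a child with samples on Day 22 and, at a compliant end-of-treatment visit, on Day 25. Both fall in Days 21-27. Distances to target 22 are 0 and 3, so the closest-to-target rule keeps Day 22. The Day 25 value is not used for change from baseline and the Day 29 row is empty. Nearest-target ranges alone would not cure this: Day 25 is 3 days from 22 and 4 from 29, so it would still be filed under Day 22.

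**Overall count for the Day 8, 15, 22 and 29 visits** (4 × 11 = 44 compliant days). The SAP ranges put 5 + 1 + 4 + 4 = 14 outside their own row, of which 2 (Days 3-4) have no row. Nearest-target ranges (to Day 11, 12-18, 19-25, 26-34) put 2 + 4 + 4 + 2 = 12 outside their own row, of which none is without a row.

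**The case against.** Windows of 11 days spaced 7 days apart overlap, so no set of disjoint day ranges can reproduce them. Every SAP post-baseline range lies inside its own visit's compliant window. From Day 15 on, each upper limit is the last compliant day (20 = 15 + 5, 27 = 22 + 5, 34 = 29 + 5, 40 = 35 + 5), which is a recognisable convention. Of the 14 days filed outside their own row, 12 are also compliant days for the row they land in. Midpoint ranges reduce the count only from 14 to 12. All of this stands. A reader might infer that filing Days 24-27 under Day 22 is an outright error, or that date ranges must give way to recorded visit labels. The documents support neither; that is a choice of convention, and the SAP says openly that subjects do not always keep to the schedule.

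A reader might also infer that compliant samples are lost on a large scale. The by-visit liver and platelet tables take the worst value in each window, so a value on Days 24-27 is still counted, under Day 22. SAP 8.4 applies the closest-to-target rule to shift analyses as well, but SAP 7.6.3 builds the shift tables from the largest or smallest value over the Treatment Period, so the visit row does not matter there. Nor do early platelet counts vanish from the safety analysis: SAP 7.6.3 also tabulates counts below 20,000 over all Treatment Period measurements, which include Days 2-4 after randomization.

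The objection does not remove the Day 2-4 gap, which overlap does not explain. It also leaves the off-midpoint cuts and the undefined end-of-study time point in place.

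**Conclusion.** The point holds in a limited form. Post-randomization platelet and liver values on up to three days (Days 2-4, for children randomized on Days 1-3) have no row and are missing from the by-visit tables. Five days (11, 19, 20, 26 and 27) go to a target that is not the nearest. A compliant end-of-treatment sample on Days 24-27 can leave a child without a Day 29 value.

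Whether that last effect reaches the end-of-study liver change depends on reading end of study as the Day 29 row. The Protocol does call the Day 29 assessment the end-of-study evaluation, but SAP 7.6.3 does not tie the summary to that row. The defect shown is therefore an undefined time point, not a demonstrated loss.

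It is tempting to say that 4/11 = 36% of end-of-treatment laboratory sets would leave the Day 29 row. That needs visits spread evenly over Days 24-34. The documents give no visit distribution. The Protocol ties visits to standard-of-care visits, and its Appendix 12 outline has treatment on Days 8, 15, 22 and 29, so clustering near the targets is more plausible. No percentage should be stated.

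The effect is confined to descriptive by-visit and end-of-study laboratory summaries. Efficacy, bleeding, shift tables and Treatment Period worst-value results do not change. Primary-endpoint imaging has its own rule (up to Day 40), and vital signs are only listed. This is a minor point, worth correcting because the correction is nearly free.

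**What to change.** 1. In SAP 8.3, start the Day 8 range on the first day after randomization.
2. Make the ranges contiguous with nearest-target cut points: first day after randomization to Day 11, then 12-18, 19-25 and 26-34. Days 33-34 are nearer to 35, but they are compliant Day 29 days and no laboratory test is scheduled at Day 35, so they stay with Day 29.
3. In SAP 7.6.3, define the end-of-study liver value as the end-of-treatment visit sample, whatever its day. This settles Days 24-25, which nearest-target ranges still place under Day 22.
4. Keep the Follow-up row. Protocol 4.5.2 and 6.6 have children with marked liver elevations tested weekly until recovery, so unscheduled values on Days 35-40 are foreseeable.

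The cost is an edit to the SAP day-range table, one sentence in SAP 7.6.3 and minor programming. No new data and no protocol change are needed.

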8.4 Multiple Measurements

Laboratory Measurements

For tabulations of changes from baseline or shift analyses, if multiple laboratory measurements are obtained within the same nominal visit, then the measurement obtained on the day closest to the target day for that nominal visit will be used; in the case of a tie, the measurement obtained on the earlier day will be used in the analyses.

For tabulations of incidence of marked abnormalities (e.g. ALT >3xULN), if multiple laboratory measurements are obtained within the same nominal visit, then the worst measurement within the nominal visit window nominal visit will be used.

9 CONTENT OF REPORTS

Statistical components for the clinical study report will be based on the content of this statistical analysis plan (SAP). Pharmacokinetic, exposure, and exploratory biomarker results may be reported separately.

Details of the tables, listings, and figures to be prepared for the final CSR will be included in a study-specific Data Presentation Plan (DPP).

10 DOCUMENT HISTORY

The document history is shown in Table 10-1

Table 10-1: Document History

Version Number	Author(s)	Description
1.0		Original Issue
2.0		Incorporated all the protocol amendments since Version 1.0 was signed off through Amendment 04, dated 08-Dec-2017. Version 2.0 was reviewed, but not signed off.
3.0		Incorporated protocol amendment 05. Modified and clarified analysis populations, including specifying primary analysis population for efficacy and safety endpoints as Randomized/Intent-to-treat. Modified sample size calculations to include calculation based on the primary analysis population. Included additional sensitivity analyses to address missing data. Clarified dosing duration and date ranges. Corrected various typographical, grammatical, and other non-content errors.
4.0		Minor modifications, including typographical, grammatical, and other non-content errors.
